5.1 SAFETY PLAN

The safety plan for patients receiving alectinib in this study is based on clinical experience and results from completed and ongoing studies in the metastatic setting as well as postmarketing experience with patients with NSCLC. For a complete summary of safety information, refer to the Alectinib Investigator's Brochure.

During the study visits conducted in the patient's homes, the following parameters will be evaluated and the investigator will use results of these procedures to assess safety throughout the study:

- Physical examinations (directed by the investigator via videoconference with the assistance of a mHCP)
- Vital signs and weight
- Laboratory tests
- ECGs

Alectinib—F. Hoffmann-La Roche Ltd 67/Protocol BO41929, Version 4 Several measures will be taken to ensure the safety of patients participating in this study. Eligibility criteria have been designed to exclude patients at higher risk for toxicities. Patients will undergo safety monitoring during study, including assessment of the nature, frequency, and severity of adverse events. In addition, guidelines for managing adverse events, dosage modification and treatment interruption or discontinuation are provided below.

5.1.1 Risks Associated with Alectinib

Events described in this section will be closely monitored and represent selected adverse events for this study.

5.1.1.1 Interstitial Lung Disease and Pneumonitis

Cases of interstitial lung disease and pneumonitis, some leading to acute respiratory distress syndrome or death, have been associated in patients receiving TKIs, including ALK inhibitors. Signs and symptoms may include dyspnea, cough, fatigue, and pulmonary infiltrates. Patients with dyspnea at rest due to complications of advanced malignancy and comorbidities may be at higher risk of pulmonary events.

Guidelines for management and follow-up of patients who develop ILD or pneumonitis are provided in Table 1.

5.1.1.2 Hepatotoxicity

Hepatobiliary findings were observed in both rat and monkey 4- and 13-week toxicity studies with alectinib at or close to clinically relevant exposures. Hepatobiliary effects included increased hepatic ALP, direct bilirubin, gamma-glutamyl transferase and liver weight, vacuolation, degeneration, and necrosis of the bile duct epithelium, inflammatory cell infiltration in Glisson's sheath, enlargement/focal necrosis of hepatocytes, and enlargement of Kupffer cells.

Abnormal hepatobiliary laboratory test values, such as increased ALT, AST, or bilirubin levels, have been observed after alectinib administration in patients. AST, ALT, and total bilirubin levels temporarily increased in the initial stages of treatment and then improved. In patients with Grade 3 and 4 AST/ALT elevations, documented drug-induced liver injury by liver biopsy was reported with uncommon frequency in alectinib pivotal clinical trials. Concurrent elevations in ALT or AST \geq 3 × ULN and total bilirubin \geq 2 × ULN, with normal ALP, occurred with uncommon frequency in patients treated in alectinib clinical trials.

In patients treated with other tyrosine kinase ALK-inhibitor drugs, abnormal liver function tests and drug-induced hepatotoxicity, including cases with fatal outcome, have been reported.

Guidelines for management and follow-up of patients who develop hepatotoxicity are provided in Table 1.

Alectinib—F. Hoffmann-La Roche Ltd 68/Protocol BO41929, Version 4

5.1.1.3 Anemia, Including Hemolytic Anemia

Hematologic findings were observed in both rat and cynomolgus monkey 4- and 13-week toxicity studies with alectinib. *The* findings were at or close to clinically relevant exposures. *Changes in red blood cell morphology (e.g., poikilocytosis, red cell fragmentation) and in the erythroid system's other parameters (e.g., reticulocyte count, hemoglobin, hematocrit, mean corpuscular volume) were seen with alectinib, but these changes were very slight, considered reversible,* and *did not exacerbate with prolonged alectinib administration.*

Cases of anemia, *including hemolytic anemia*, have been reported in patients treated with alectinib; the majority of the events were Grade 1 and 2.

Guidelines for *anemia* (*including hemolytic anemia*), adverse events' management, and follow-up are provided in Table 1.

5.1.1.4 Gastrointestinal Disorders

Gastrointestinal disorders such as nausea, vomiting, constipation, diarrhea, and stomatitis have been reported with alectinib. Similar GI disorders have been observed with other TKIs, including ALK inhibitors.

Sodium lauryl sulfate (SLS) is a surfactant excipient in the clinical formulation at a concentration of 50% (weight per weight SLS to active pharmaceutical ingredient). This excipient is a known GI irritant and may be associated with GI adverse events, including nausea, vomiting, diarrhea, and abdominal pain. Of note, GI tract toxicity due to SLS is not because of systemic toxicity but is a consequence of local irritation to the GI tract. In general, tolerability is improved when SLS is administered together with food.

Guidelines for management and follow-up of patients who develop GI disorders are provided in Table 1.

5.1.1.5 Skin Disorders

Skin rash has been reported with the majority of TKIs, including those targeting the ALK receptor (Hartmann et al. 2009).

Results of an in vitro phototoxicity study indicated that alectinib may have phototoxic potential, and cases of skin rash and photosensitivity (generally Grades 1 and 2) have been reported with alectinib.

Guidelines for management and follow-up of patients who develop skin disorders are provided in Table 1.

5.1.1.6 Vision Disorders

In the rat quantitative whole body autoradiography study, tissue radioactivity disappeared over time, following a time course comparable with that of plasma radioactivity, except for melanin-containing tissues such as uveal tract of eyes, which

Alectinib—F. Hoffmann-La Roche Ltd

had much higher and more sustained exposure in pigmented rats. This is consistent with what is commonly observed with lipophilic basic drugs.

Vision disorders, including diplopia, photopsia, blurred vision, visual impairment, and vitreous floaters, have been reported with several TKIs, including ALK inhibitors (crizotinib) (Shaw et al. 2013).

Vision disorders, such as blurred vision, visual impairment, vitreous floaters, reduced visual acuity, asthenopia, and diplopia, have been reported with alectinib and were generally Grades 1 and 2.

Guidelines for management and follow-up of patients who develop vision disorders are provided in Table 1.

5.1.1.7 Edema

Most TKIs, including ALK-inhibitor crizotinib, have been associated with edema. Events of edema (mainly peripheral edema) have been reported with alectinib, mostly Grades 1 and 2.

Guidelines for management and follow-up of patients who develop edema are provided in Table 1.

5.1.1.8 Bradycardia

In the cynomolgus monkey telemetry study, there were no effects on the ECG, any of the other cardiovascular parameters, or body temperature at doses of up to 15 mg/kg alectinib.

In a preliminary non–Good Laboratory Practice telemetry study in conscious cynomolgus monkeys, there were no effects of alectinib on ECG or heart rate observed.

Events of bradycardia have been reported with alectinib. Data based on ECG and pulse measurements from alectinib clinical trials show a decrease in heart rate during alectinib treatment, which is mainly asymptomatic. In patients treated with other ALK inhibitors (crizotinib and ceritinib), bradycardia adverse events, as well as decreases in heart rate based on ECG and pulse measurements, have also been reported (Xalkori U.S. Package Insert).

In case of bradycardia, concomitant medications must be evaluated to identify those that are known to cause bradycardia, as well as anti-hypertensive medications, and discontinuation or dose reduction of these concomitant medications must be considered.

In case of bradycardia adverse event related to alectinib, refer to adverse event grade-dependent rules for dose modification outlined in Table 1.

5.1.1.9 Abnormal Renal Function (Serum Creatinine Increased, Acute Kidney Injury)

In the 2-week, nonclinical primate study at 60 mg/kg alectinib, an increase in creatinine was observed, but no changes were observed in histopathology. In all other nonclinical primate studies, no changes in creatinine were observed.

Serum creatinine increases have been reported with alectinib treatment with common frequency. Acute kidney injury, including fatal outcome, has been observed with uncommon frequency in patients treated in alectinib clinical trials.

Serum creatinine increases and/or decreases in glomerular filtration rate, renal failure, and/or renal impairment have been reported for other ALK inhibitors.

Guidelines for management and follow-up of patients who develop abnormal renal function are provided in Table 1.

5.1.1.10 Severe Myalgia and CPK Elevations

Post-marketing experience with some TKIs includes reports of myopathy and rhabdomyolysis (Hohenegger 2012).

Blood CPK increases, generally Grades 1 and 2, and muscular adverse events have been reported with alectinib treatment. Grade 3 myalgia and CPK elevations were reversible upon dose reduction and interruption.

Guidelines for management and follow-up of patients who develop severe myalgia and CPK elevations are provided in Table 1.

5.1.1.11 Dysgeusia

Events of dysgeusia have been reported with ALK inhibitors. With alectinib, these are generally of Grades 1 and 2 severity. All patients who experienced dysgeusia continued alectinib treatment without any dose modification.

In case of dysgeusia adverse event related to alectinib, refer to adverse event grade-dependent rules for dose modification outlined in Table 1.

5.1.1.12 Alkaline Phosphatase Increase

Cases of increased blood ALP have been observed after alectinib administration. The majority of the cases were of Grades 1 and 2 severity.

In patients treated with other ALK inhibitors, increased blood ALP has been reported.

In case of ALP increase adverse event related to alectinib, refer to adverse event grade-dependent rules for dose modification outlined in the first section of Table 1.

5.1.2 Management of Patients Who Experience Adverse Events

5.1.2.1 Dose Modifications

The dose of alectinib can be reduced in steps of 150 mg up to two times for the management of drug-related toxicities (i.e., from 600 mg BID to 450 mg BID, and then from 450 mg BID to 300 mg BID):

Dose Reduction Schedule	Dose Level
Dose	600 mg twice daily
First dose reduction	450 mg twice daily
Second dose reduction	300 mg twice daily

If further dose reduction is indicated after two dose reductions, the patient must discontinue alectinib. Administration of a dose below 300 mg BID is not allowed in this study.

5.1.2.2 Treatment Interruption

Alectinib treatment may be temporarily suspended in patients who experience toxicity considered to be related to study drug. If alectinib has been withheld for >21 days because of toxicity, the patient should be discontinued from alectinib, unless resumption of treatment is *approved by the* investigator *following consultation* with the Medical Monitor *if needed*. Alectinib treatment may be suspended for reasons other than toxicity (e.g., surgical procedures), *at the investigator's discretion,* following consultation with the Medical Monitor *if needed*. The investigator *may consult the Medical Monitor to determine* the acceptable length of treatment interruption.

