5.1.2.3 Management Guidelines

Table 1Guidelines for Management of Risks, Adverse Events, and
Selected Laboratory Abnormalities with Alectinib

Event	Action to Be Taken	
All AEs related ^a to alectinib (unless otherwise specified in this table) + hepatotoxicity AEs (irrespective of relatedness)	Grade 4: Femporarily interrupt alectinib for a maximum of 21 days after which the drug must be permanently withdrawn. If improvement o Grade ≤ 1 or baseline does not occur within 3 weeks, bermanently discontinue alectinib. First episode: If improvement to Grade ≤ 1 or baseline within 21 days, decrease the current dose of alectinib by 150 mg 1 capsule) BID. Second episode: If improvement to Grade ≤ 1 or baseline within 21 days, decrease the current dose of alectinib by another 150 mg (1 capsule) BID. Third episode: Permanently discontinue alectinib. Please note that dose should not be reduced below 300 mg BID. Grade 3: Temporarily interrupt alectinib for a maximum of 21 days after which drug must be permanently withdrawn. First episode: If improvement to Grade ≤ 1 or baseline occurs within 10 days alectinib may be restarted at the original dose or dose reduced by 150 mg (1 capsule) at the investigator's discretion. If improvement to Grade ≤ 1 or baseline occurs after 10 days but within 21 days then alectinib dose must be decreased by 150 mg (1 capsule BID). Second episode: If improvement to Grade ≤ 1 or baseline occurs within 10 days alectinib may be restarted at the original dose or dose reduced by 150 mg (1 capsule) at the investigator's discretion. If improvement to Grade ≤ 1 or baseline occurs after 10 days but within 21 days then alectinib dose must be decreased by 150 mg (1 capsule BID). Second episode: If improvement to Grade ≤ 1 or baseline occurs within 21 days, decrease the current dose of alectinib by 150 mg (1 capsule) BID. Third episode: Permanently discontinue alectinib. Grade 2: To be managed at the investigator's discretion. Please note that alectinib cannot be interrupted for more than 21 days and cannot be dose reduced below 300 mg BID. Grade 1: No action required	
Interstitial lung disease/ pneumonitis	Patients should be monitored for pulmonary symptoms indicative of interstitial lung disease/pneumonitis.	
	Regardless of relatedness to alectinib , study drug should be permanently discontinued in patients diagnosed with interstitial lung disease/pneumonitis of any grade.	

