Hepatotoxicity	Liver test laboratory abnormalities are to be reported as AEs only if fulfilling the criteria listed in Section 5.3.5.4 and Section 5.3.5.6. At any time during the study treatment, if symptoms compatible with liver injury are observed, liver enzymes should be measured as soon as possible.	

Event	Action to Be Taken	
Hepatotoxicity (cont.)	Regardless of relatedness to alectinib , the grade-dependent rules for dose interruptions and dose modification outlined in the first section of this table must be followed.	
	In addition, study drug treatment has to be permanently discontinued if any of the following occurs:	
	• First observation of ALT or AST >8 × ULN	
	 ALT or AST >5× ULN for more than 2 weeks 	
	 First observation of ALT or AST >3× ULN and total bilirubin >2×ULN 	
	 First observation of ALT or AST >3× ULN and the appearance of jaundice or signs of hepatic dysfunction or other symptoms (such as fatigue, nausea, vomiting, right upper quadrant pain or tenderness, fever, rash, or eosinophilia [>5%]) 	
	 Following study drug discontinuation, weekly monitoring of laboratory values should continue until the abnormal values have normalized to pretreatment levels and/or an adequate explanation of the abnormal value is found 	
	 Resumption of study drug is not allowed in patients discontinuing because of any of the above criteria 	
Gastrointestinal tract AEs (e.g., nausea, vomiting, diarrhea, stomatitis)	The events are expected to be minimized by taking the study drug with a meal. If GI events occur, appropriate measures should be taken in accordance with local clinical practice guidelines.	
	In case of AEs related to alectinib, follow the grade-dependent rules for dose interruption and modification outlined in the first section of this table.	
Skin disorder AEs (e.g., phototoxicity, rash)	 Patients should be advised to avoid prolonged sun exposure while taking alectinib and for at least 7 days after study drug discontinuation. Patients should also be advised to use a broad-spectrum sunscreen and lip balm of at least SPF 50 to help protect against potential sunburn during this period. In case of AEs related to alectinib, follow the grade-dependent rules for dose interruption and modification outlined in the first section of this table. 	

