Vision disorders	Investigators should consider referring the patients for an ophthalmologic evaluation according to local clinical practice guidelines if vision disorders persist or worsen in severity and to advise patients to exercise caution when driving or operating machinery due to the risk of developing a vision disorder.	
	In case of AEs related to alectinib, follow the grade-dependent rules for dose interruption and modification outlined in the first section of this table.	

Table 1Guidelines for Management of Risks, Adverse Events, and
Selected Laboratory Abnormalities with Alectinib (cont.)

Table 1Guidelines for Management of Risks, Adverse Events, and
Selected Laboratory Abnormalities with Alectinib (cont.)

Event	Action to Be Taken	
Edema	Physical examinations will be performed routinely in clinical trials In case edema events occur, appropriate measures should be ta in accordance with local clinical practice guidelines.	
	In case of AEs related to alectinib, follow the grade-dependent rules for dose interruption and modification outlined in the first section of this table.	
Abnormal renal function AEs	Kidney function laboratory abnormalities are to be reported as AEs if they fulfill the criteria listed in Section 5.3.5.4.	
	If at any time during the study treatment serum creatinine increases by $\ge 2 \times$ over the baseline-visit value, the patient has to be carefully monitored. All underlying factors that may have acutely impacted serum creatinine levels need to be evaluated and corrected (e.g., dehydration, recent exposure to contrast media, increased amount of cooked meat in diet, concomitant medications affecting renal function as appropriate, etc.).	
	Any serum creatinine value that is increased by $\ge 2 \times$ over the baseline-visit value requires repeat testing.	
	• For Grade 1 and Grade 2 AEs related to alectinib, follow the grade-dependent rules for dose interruption and modification outlined in the first section of this table.	
	• For Grade 3 AEs related to alectinib, temporarily interrupt alectinib until serum creatinine recovers to Grade 1 or baseline, then resume at reduced dose.	
	• For Grade 4 AEs related to alectinib, permanently discontinue study drug.	
Severe myalgia and CPK elevations	CPK laboratory abnormalities are to be reported as AEs if they fulfill the criteria listed in Section $5.3.5.4$.	

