	Myopathy should be considered in any patient with diffuse myalgia, muscle tenderness or weakness, and/or marked elevations of CPK levels. Patients should promptly report unexplained muscle pain, tenderness, or weakness, particularly if accompanied by malaise or fever. CPK levels should be monitored in patients reporting these symptoms.	
	In case of AEs related to alectinib, follow the grade-dependent rules for dose interruption and modification outlined in the first section of this table.	

Table 1	Guidelines for Management of Risks, Adverse Events, a		
	Selected Laboratory Abnormalities with Alectinib (cont.)		

Bradycardia ^b	Grade 2 or Grade 3	
	 Temporarily withhold for a maximum of 21 days (after which the drug must be permanently withdrawn) until recovery to ≤ Grade 1 (asymptomatic) bradycardia or to a heart rate of ≥ 60 bpm. Evaluate concomitant medicinal products known to cause bradycardia, as well as anti-hypertensive medicinal products. If a contributing concomitant medicinal product is identified and discontinued, or its dose is adjusted, resume at previous dose upon recovery to ≤ Grade 1 (asymptomatic) bradycardia, or to a heart rate of ≥ 60 bpm. 	
	If no contributing concomitant medicinal product is identified, or if contributing concomitant medicinal products are not discontinued or dose modified, resume at reduced dose upon recovery to \leq Grade 1 (asymptomatic) bradycardia or to a heart rate of \geq 60 bpm.	
	Grade 4	
	 Permanently discontinue if no contributing concomitant medicinal product is identified. 	
	 If a contributing concomitant medicinal product is identified and discontinued, or its dose is adjusted, resume at reduced dose upon recovery to ≤ Grade 1 (asymptomatic) bradycardia or to a heart rate of ≥ 60 bpm within 21 days, with frequent monitoring as clinically indicated. 	
	Permanently discontinue in case of recurrence.	

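### Protocol 5.1.2.2 allows alectinib to restart after more than 21 days off for toxicity, but the general and bradycardia rows of Table 1 do not; the default intervals before palliative radiation in 4.5.1 and 4.5.3 also disagree

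*Protocol*

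**What the plan says.** **Interruption for toxicity.** Protocol 5.1.2.2 sets a default with an exception: "If alectinib has been withheld for >21 days because of toxicity, the patient should be discontinued from alectinib, unless resumption of treatment is"; the exception then turns on investigator approval, with the Medical Monitor consulted if needed.

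Table 1 in Protocol 5.1.2.3 covers the same holds grade by grade.

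- General row, Grade 4: "interrupt alectinib for a maximum of 21 days after which the drug must be permanently withdrawn".
- General row, Grade 3: "Temporarily interrupt alectinib for a maximum of 21 days after which drug must be permanently withdrawn".
- General row, Grade 2: managed at the investigator's discretion, but "Please note that alectinib cannot be interrupted for more than 21 days and cannot be dose reduced below 300 mg BID".
- Bradycardia row, Grade 2 or 3: "Temporarily withhold for a maximum of 21 days (after which the drug must be permanently withdrawn").
- Bradycardia row, Grade 4, where a contributing concomitant product has been stopped or adjusted: treatment may resume on recovery "within 21 days, with frequent monitoring as clinically indicated".

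Neither row refers to 5.1.2.2. The general row gives way only to what Table 1 itself specifies differently. Section 4.7.1 requires permanent discontinuation when a stopping criterion in Section 5.1.2 is met.

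**Palliative radiation.** Section 4.5.1 lets radiation begin inside the 24 hours after the last alectinib dose, unless the investigator judges that safety calls for a longer washout. Section 4.5.3 says alectinib should be held for 24 hours or more before radiation. It allows exceptions if the rationale is discussed with the Sponsor's clinical pharmacologist and documented.

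**The concern.** Protocol 5.3.1.1 tells the investigator to apply medical judgment and the protocol's dose modification rules. Once a toxicity hold passes day 21, those rules give two answers: stop permanently, or restart with approval. An investigator who stops breaches neither passage. One who restarts has written support in 5.1.2.2 and a written bar in Table 1. Two sites can each point to the protocol and handle similar patients differently.

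Three things are at stake.

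- Safety management may be inconsistent across sites, in a study run largely by telemedicine.
- It becomes unclear what counts as a deviation. Section 9.2 does not allow prospective requests to deviate, and Protocol 6.2 and SAP 5.7.1 report major deviations, so the text should settle whether a late restart is one.
- The descriptive summaries are affected: drug exposure (SAP 5.6.1), and adverse events leading to withdrawal versus those leading to reduction or interruption (SAP 5.6.2).

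The radiation passages raise the same problem on a smaller scale.

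**Working it through.** The plan gives no figure to reproduce. The check sets the rules side by side and applies them to test cases.

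**Step 1: a toxicity hold with recovery on day 25** (25 − 21 = 4 days past the limit).

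| Source | Outcome at day 25 |
|---|---|
| 5.1.2.2 | Restart possible with investigator approval |
| Table 1 general, Grade 4 | Permanent withdrawal |
| Table 1 general, Grade 3 | Permanent withdrawal |
| Table 1 general, Grade 2 | Interruption of this length not allowed |
| Table 1 bradycardia, Grade 2 or 3 | Permanent withdrawal |
| Table 1 bradycardia, Grade 4, contributing product addressed | Condition for resuming not met |

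All five Table 1 rules differ from 5.1.2.2. On day 20 there is no disagreement, because the 5.1.2.2 exception applies only after day 21.

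**Step 2: does another passage settle it?** Section 4.7.1 does not, because Section 5.1.2 contains both texts. The general row's carve-out does not, because it is confined to the table and 5.1.2.2 lies outside it.

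**Step 3: how far does the conflict reach?** Several other rows (gastrointestinal, skin, vision, edema, myalgia and CPK, hepatotoxicity, non-hemolytic anemia) send the reader back to the general row and inherit the conflict. Three provisions lie outside it:

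- Renal Grade 3 states no 21-day limit: "For Grade 3 AEs related to alectinib, temporarily interrupt alectinib until serum creatinine recovers to Grade 1 or baseline, then resume at reduced dose".
- Confirmed hemolytic anemia states none either.
- The hepatotoxicity stopping criteria have their own explicit rule: "Resumption of study drug is not allowed in patients discontinuing because of any of the above criteria".

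**Step 4: palliative radiation.** Let t be the hours from last dose to radiation. The 4.5.1 default is t ≤ 24 and the 4.5.3 default is t ≥ 24; they meet only at t = 24.

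- t = 12: the 4.5.1 default is met. The 4.5.3 default is not, unless an exception is documented.
- t = 30: 4.5.3 is met, and 4.5.1 is not breached because it is permissive.

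The routes for departing from each default also differ: investigator judgment in 4.5.1, documented discussion with the clinical pharmacologist in 4.5.3. The sponsor notification in 4.5.1 sets no interval.

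**Step 5: how many patients?** The documents give no rate of holds longer than 21 days and no rate of palliative radiotherapy. Protocol 1.2.2 does report, for alectinib in lung cancer, interruption due to adverse events in 19% of patients in the randomized first-line trial and dose modification or interruption in 33% in the pooled single-arm studies. If similar rates held among 50 patients, 0.19 × 50 = 9.5 and 0.33 × 50 = 16.5, so about 10 to 17 would have any such event. Holds beyond 21 days would be an unknown subset, so this range indicates an upper bound only.

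**The case against.** The strongest reply is that the texts can be harmonized. On that reading 5.1.2.2 is the general rule, Table 1 governs wherever it states its own limit, and the exception operates only where Table 1 sets none, such as renal Grade 3 or hemolytic anemia. Likewise, waiting 24 hours or more before radiation satisfies both radiation passages. This is a reasonable way to resolve the conflict, but neither document states that precedence. An investigator who relies on the exception in 5.1.2.2 is still following written text.

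Table 1 is also titled as guidelines. The rows at issue, however, mostly use mandatory language about withdrawal and interruption.

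Two narrower points stand. The Grade 4 bradycardia rule states only a condition for resuming and is silent about later recovery, so the conflict there is inferred rather than explicit. And five is a count of rules, not of phrases to edit. The two rows contain about ten 21-day phrases: four at general Grade 4 (including a separate 3-week discontinuation sentence), three at Grade 3, one at Grade 2 and two for bradycardia (4 + 3 + 1 + 2 = 10).

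It can also be argued that the qualifier on exceptions in the opening of 4.5.3 covers the whole prohibition rather than only its time period, or that the clinical pharmacologist clause does not reach the 24-hour hold. Either reading still leaves the two radiation defaults different.

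**Conclusion.** The concern holds on both parts. For toxicity holds longer than 21 days, 5.1.2.2 and the general and bradycardia rows of Table 1 give different rules, and nothing in the protocol says which governs. Sections 4.5.1 and 4.5.3 set different default intervals before palliative radiation.

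The statistical consequence is modest. The primary estimand handles early treatment discontinuation by treatment policy (SAP Table 2), and tumor assessments continue off treatment until progression (Protocol 4.6.5 and 4.7.1), so the effect on confirmed response rate should be limited. The affected safety outputs are descriptive. The number of patients involved is not known. The inconsistency should be corrected because it concerns rules for stopping and restarting study drug; it does not threaten the primary result.

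**What to change.** By protocol amendment:

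1. Reconcile 5.1.2.2 with the Table 1 general row (Grades 2, 3 and 4) and the bradycardia row (Grade 2 or 3, and Grade 4), so that all state the same limit and the same exception, or no exception. Check every 21-day or 3-week phrase in those rows, including the episode-level restart conditions.
2. Reconcile 4.5.1 with 4.5.3 so that both state the same interval between alectinib and palliative radiation and the same route for departing from it.

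Which rule applies in each case is the sponsor's clinical decision.

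The cost is wording: 5.1.2.2, two rows of Table 1, and about one sentence each in 4.5.1 and 4.5.3. No new procedures or data collection are needed. Section 9.7 requires IRB/EC approval, and regulatory approval as locally required, before such a change takes effect, so a letter to sites alone would not be enough.
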